The patients and caregivers will be invited and will use the system individually. To determine effect on patients and caregivers, respectively, if a patient is recruited, we will not invite his/her caregiver, and vice versa. Both patients and caregivers will be randomly assigned into an experimental group (receiving the computerized knowledge and education system) or a control group (receiving additional rehabilitation) using numbers randomly generated by a computer. Allocation concealment will be applied. All the participants will be tested by the knowledge system at the beginning of the study, 4 weeks after inception of the study, and 3 months after inception of the study. All the testing will be administered by a research assistant who will be unaware of study-group assignment.

Regarding the sample size needed for this study, a difference of 20% on stroke and OT knowledge in favor of the experimental group will be expected. In addition, we expect that about 70% of the participants will complete all assessments. Therefore, about 25 patients and 25 caregivers will be required for each arm of the trial to achieve a sufficient statistical power of 80%.

Protocols for the experimental and control groups:

The patients/caregivers assigned to the experimental group will first receive the computerized adaptive knowledge testing system. They will be then given adaptive educational materials provided by the educational system according to their testing results. The participants will be instructed to read or

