100 sub-acute patients (including inpatients and outpatients) will be recruited from the National Taiwan University Hospital. The patients will meet the criteria (both inclusion and exclusion criteria) mentioned in the phase 4 study. Their caregivers will also be invited to participate.

Power analysis

A difference of 2 points (about 10%) on the Barthel index in favor of the experimental group will be regarded as clinically relevant.⁵⁷ In addition, we expect that about 70% of the participants will complete all assessments. Therefore, about 50 patients will be required for each arm of the trial to achieve a sufficient statistical power of 80%.

Procedure:

The patients will be randomly assigned into an experimental group (receiving the patient-centered program) or a control group (receiving additional rehabilitation). Allocation concealment will be applied. All participants will be assessed by trained raters at the beginning of the study, 4 weeks after inception of the study, 3 months after inception of the study, and 1 year after inception of the study. The raters will be unaware of study-group assignment. The cost of each group will be recorded.

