The stroke rehabilitation assessment of movement (STREAM)⁵⁹ instrument consists of 30 items that are equally distributed among 3 subscales: upper-limb motor function, lower-limb motor function, and mobility. Motor function is scored on a 3-point scale (0: unable to perform the test movement; 1: able to only partially perform the test movement; and 2: able to complete the test movement). Mobility is scored on a 4-point scale similar to that used for scoring limb movements except that a category has been added to allow for independence with the help of a mobility aid. Thus, the maximum raw total STREAM score is 70, with each of the limb subscales scored out of 20 points and the mobility subscale scored out of 30 points. We have validated the STREAM thoroughly in stroke patients.⁶⁰⁻⁶⁴

Primary outcome measures:

The Frenchay Activities Index (FAI)⁶⁵ was developed to measure social function and instrumental activities of daily living following stroke. It comprises 15 items related to normal activities: preparing

meals, washing up, washing clothes, light housework, heavy housework, local shopping, social outings, walking outside for more than 15 minutes, actively pursuing hobbies, driving/bus travel, outings/car rides, gardening, household/car maintenance, reading books, and gainful employment. The total possible score of the FAI ranges from 0 to 45. The FAI is reliable and valid in assessing social function for patients with stroke.⁶⁵⁻⁶⁷

The Barthel ADL Index (BI)⁶⁸ and the FAI scores can be combined to represent comprehensive activities of daily living (CADL) function, representing the entire continuum of disability.⁶⁹ The CADL contains 10 items of the BI and 13 items of the FAI (with 2 misfit items of the FAI deleted to fit the Rasch model).⁶⁹ The Rasch-transformed interval score of the CADL proposed by Hsueh et al.⁶⁹ will be used in this study.

We will also use the computerized adaptive ADL test which was developed by our research group. The computerized adaptive ADL test is efficient and valid to assess ADL and IADL in stroke patients.⁷⁰ The computerized adaptive ADL test is particularly useful for the patients in our country because it is the only ADL/IADL measure developed for stroke patients in Taiwan. Particularly, some IADL items are specific to cultural differences.⁷¹

Secondary outcome measures:

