The participants in the control group will not be given the results of testing. However, oral explanations will be given by the research assistant if they have questions about the testing. These participants in the control group will be offered additional rehabilitation programs to serve as placebo. The time of the additional rehabilitation program will be similar to the time that the participants spend taking part in the experimental group, which we expect to be about 2 hours per week for 3 consecutive weeks.

Data analysis:

Baseline characteristics will be reported by descriptive statistics (e.g., mean and SD for continuous variables, or frequency tabulations for categorical variables) for each group. Homogeneity of both groups at the baseline (time 1) will be examined using a Student's t test or Mann-Whitney U test where appropriate. If there are between significant differences between both groups, statistical control (e.g., analysis of covariance, ANCOVA) will be applied for further analysis of effectiveness.

The primary analysis of effectiveness (full-analysis set) will consist of a comparison of the change scores between time 2 to time 1 and time 3 to time 2 in primary and secondary outcome measures. Analysis of variance (ANOVA) will be used to compare the change scores between groups. The analyses will be adjusted using ANCOVA for any significant differences at baseline. Intention-to-treat analysis will be applied. Alpha level will be set at 0.05. The statistical analyses will be done by use of SPSS (version 16.0).

Incremental cost-effectiveness ratios will be calculated as cost per QALY to assess the cost-effectiveness of the different programs.

(F) Anticipated Results

We expect that the patients and caregivers' original knowledge of stroke and OT would be limited or modest. Our adaptive knowledge and education system will efficiently improve their knowledge of stroke and OT. We anticipate that the CATs for stroke and OT knowledge can reach an overall reliability above 0.95 (i.e., excellent reliability) and require less than 10 minutes to administer or test fewer than 20 items to ensure its efficiency.

Furthermore, the patient-centered OT program using the adaptive knowledge and education system will improve ADL independence in stroke patients. The patient-centered OT program will be cost-effective in increasing ADL function and quality-adjusted life years.

Significance:

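### Phase 6: the 80% power is stated for the raw Barthel Index, which is not a listed primary outcome, without an SD, and no single primary outcome or contrast is named

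*Protocol*

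**What the plan says.** All references are to section (E) of the Protocol.

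- **Phase 6, Power analysis.** "A difference of 2 points (about 10%) on the Barthel index in favor of the experimental group will be regarded as clinically relevant". The text adds that "we expect that about 70% of the participants will complete all assessments" and concludes: "Therefore, about 50 patients will be required for each arm of the trial", for 80% power. No SD is given.
- **Phase 6, Primary outcome measures.** Three measures are described. The first is the FAI, scored 0 to 45. Next, the Barthel Index and FAI "scores can be combined to represent comprehensive activities of daily living (CADL) function, representing the entire continuum of disability"; the CADL has 10 Barthel and 13 FAI items, and its Rasch-transformed score is the one to be used. Third: "We will also use the computerized adaptive ADL test which was developed by our research group".
- **Phase 6, Data analysis.** The primary analysis compares change scores from time 1 to time 2 and from time 2 to time 3, in both the primary and the secondary measures (EQ-5D and SS-QOL), by ANOVA. The only statement on error control is "Alpha level will be set at 0.05".
- **Phase 4, Procedure.** The sample size rests on the expectation that "a difference of 20% on stroke and OT knowledge in favor of the experimental group will be expected", again without an SD. The Rasch analysis text under Phase 2 says that logit scores will be used in the data analysis that follows.

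**The concern.** A power statement is useful only if it refers to the test on which the trial will be judged. Here it refers to raw Barthel points. A 2-point difference does not convert into FAI points, CADL Rasch units or an adaptive-test score without further data, and no effect size or SD is given for any of the three. The power for every listed primary outcome is therefore unknown.

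The primary analysis also has no lead outcome and no lead interval. A reader of the results could not tell from the protocol which comparison decides whether the programme works. The trial's efficacy conclusion depends on settling both points before the data are seen.

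**Working it through.** **1. The plan's own figure.** Inputs from the Power analysis paragraph: difference 2 points, 70% completion, 50 per arm, power 80%. From Data analysis: alpha 0.05, taken here as two-sided (sidedness is not stated).

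Dropout step: 50 × 0.70 = 35 completers per arm, and 35 / 0.70 = 50, so this step is consistent. The 80% cannot be reproduced without an SD, so the formula is solved for the SD instead.

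Detectable standardised difference: d = (1.960 + 0.842) × √(2/n), and SD = 2/d.

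| n per arm | d (normal) | SD (normal) | d (t test) | largest SD for 80% (t test) |
|---|---|---|---|---|
| 35 | 2.802 × 0.239 = 0.670 | 2.99 | 0.679 | 2.94 |
| 50 | 2.802 × 0.200 = 0.560 | 3.57 | 0.566 | 3.53 |

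The two rows are bounds. The 70% refers to completing all assessments, including the 1-year visit, whereas the primary analysis ends at 3 months. The number with data at 3 months may therefore lie anywhere from 35 to 50.

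Power for 2 points by noncentral t, with non-centrality (2/SD) × √(n/2). The SDs are assumptions chosen only to show sensitivity:

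| assumed SD of change | 35 per arm | 50 per arm |
|---|---|---|
| 2.5 | 91.0% | 97.7% |
| 3 | 78.5% | 91.0% |
| 3.5 | 65.4% | 80.8% |
| 4 | 54.1% | 69.7% |
| 5 | 37.8% | 50.8% |

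**2. Match between the powered variable and the planned tests.** The planned tests are on the FAI, the CADL Rasch score and the adaptive test, plus the secondary measures. The Barthel Index enters only as 10 of the 23 CADL items (10 + 13). No section plans a test of its raw total.

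**3. Number of tests and false-positive rate.** Suppose there is no effect on any measure, each test is two-sided at 0.05, and any one significant primary test counts as success.

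- Three primaries × two intervals = 6 tests. If independent: 1 − 0.95⁶ = 26.5%.
- Two primaries (CADL and adaptive test only) × two intervals = 4 tests. If independent: 1 − 0.95⁴ = 18.5%.

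The measures overlap, so a multivariate-normal simulation was run with assumed correlations between outcomes. The correlation between the two interval changes was set at −0.5 and at 0, which gives the two ends of each range.

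| correlation between outcomes | 6 tests | 4 tests |
|---|---|---|
| 0 | 25-26% | 17-19% |
| 0.5 | 22-24% | 16-17% |
| 0.8 | 17-19% | 14-15% |

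**4. Phase 4.** 25 × 0.70 = 17.5 completers per arm in each population. By t test, 80% power needs d of about 0.98. Whether a 20% knowledge difference is that large on the logit scale cannot be judged, because neither the difference nor its SD is given in logits.

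**The case against.** Several objections limit how far the point goes.

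- **The success rule is not written down.** A reader might infer that the trial has a false-positive rate of 17-26%. The protocol does not say that any one significant test suffices. If all primaries had to be significant, alpha would not be inflated and joint power would suffer instead. A statistical analysis plan, not shown, might add a multiplicity rule. This stands, so the rates are conditional. What the protocol itself fixes is a primary analysis spanning all measures and two intervals.
- **The count of primaries is a reading.** The FAI and the Barthel Index can be seen as components of the CADL, which leaves two primaries. This stands, and is why both counts are shown.
- **Underpowering is not shown.** A reader might infer from the rows for SD 4 and 5 that the trial is too small. The relevant SD is that of change scores, and nothing in the document makes a value near 3 implausible. The table shows that 80% is unverified, not that it is wrong.
- **35 is a lower bound** for data at 3 months, given intention-to-treat analysis and the imputation that the Phase 2 data analysis extends to the remaining parts of the project. This stands.
- **The Barthel Index is not unrelated to a primary outcome,** since it supplies 10 CADL items. True, but power for one component's raw total does not carry over to the combined Rasch score.
- **The Phase 4 figure** might be read as a difference in proportions. The planned analysis there is ANOVA on change scores, so the text does not support that reading.

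None of this removes the mismatch between the powered variable and the listed outcomes.

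**Conclusion.** The point holds and should be corrected in the protocol. The stated 80% power attaches to a score that no planned primary test uses. Even for that score it holds only if the SD of the analysed change is at most 2.94 (35 per arm) to 3.53 (50 per arm), and no SD is stated. Power for the FAI, the CADL score and the adaptive test cannot be calculated from the document.

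The primary analysis names no lead outcome or interval. Under an any-one-suffices rule, the false-positive rate would be about 17-26% for three primaries or 14-19% for two, for correlations between outcomes from 0.8 down to 0. Under an all-must-succeed rule, the loss would be in power. The protocol adopts neither rule, so the document supports neither an inflated alpha nor an underpowered trial as an established fact. It does support the conclusion that the efficacy claim has no defined test and no power figure of its own.

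**What to change.** 1. In Phase 6, name one primary outcome: either the Rasch CADL score, or the Barthel Index if the sponsor prefers it, in which case it must be listed as primary.
2. Name one contrast. Use one of the two already planned, or amend Data analysis to change from baseline to 3 months, which is neither of the present contrasts.
3. Make the other measures and intervals secondary, or test them in a fixed order.
4. Keep 50 per arm. Restate the power for the named primary with a sourced or assumed SD, shown as a range, and with the number expected to have data at that visit.
5. In Phase 4, state the 20% difference and its SD on the Rasch logit scale, and report the power that 25 per arm gives (about 17 to 18 completers, detectable standardised difference about 0.98).

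The cost is protocol wording and a recalculation, with no extra patients. The restated power may be less favourable, some measures lose primary status, and an SD must come from data outside this document.

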We will determine cost-effectiveness by relating the costs to the effects of the program. The effects will be expressed as quality-adjusted life years (QALYs), which are measured by the EQ-5D. The costs include the costs related to resource use of primary care clinicians, secondary care appointments, admissions to health care facilities, community-based support, and individual out-of-pocket expenditure (direct costs). The direct cost estimates will be based on the costs of hospital stay and follow-up rehabilitation care. Medication costs and costs related to assistive devices and adaptations in and around the house will also be included. The costs of productivity losses (indirect costs) will not be counted because most stroke patients are retired. The incremental cost-effectiveness ratio will be calculated by dividing the mean difference in costs by the mean difference in effect (as measured by the EQ-5D) between the two groups. Costs will be evaluated by having each patient keep a cost diary for the first 24 weeks after randomization. A research assistant will check the diary every other day to ensure the integrity of recording (including the time spent on each kind of professional care). The hourly costs of specialists (including physicians, physical therapists, occupational therapists, and speech and language therapists) will be calculated using the salary schedules at the National Taiwan University Hospital.

The patient-centered program will last for 6 weeks. We expect that the therapist will spend 2-4 hours on each patient per week. For the control group, we will provide 2-hour OT per week in addition to the original OT. The content of the original and additional OTs will be recorded for both groups.

Neurobehavioral conditions of the patients:

The NIHSS⁵¹ will be used to indicate stroke severity in the study sample. The NIHSS is a well validated and commonly used stroke impairment scale that sums the scores from individual elements of the neurological examination to provide an overall stroke severity score.^{51,58}

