The EuroQol is a generic measure of quality of life (QoL) and consists of a health status profile in five domains (EQ-5D), including two that are directly related to self-care and mobility.⁷² The EuroQol has been validated for use in stroke patients.⁷³ The advantage of the EuroQol is that it can be transformed into a utility score, allowing cost-utility analysis.^{43, 72}

The Stroke-Specific Quality of Life (SS-QOL)¹ is the first HRQOL measure designed to capture all domains meaningful for stroke patients. The original developers constructed the domains and items of the SS-QOL on the basis of patient interviews. It originally included 49 items from 12 domains. We have reported that construct validity of the 12-domain SS-QOL is well supported for measuring HRQOL in ischemic stroke patients.⁷⁴

Treatment protocols for the experimental and control groups:

The patients assigned to the experimental group will first receive the computerized adaptive knowledge testing system. They will be then given adaptive educational materials provided by the educational system according to their testing results. The participants will be instructed to read or watch the educational materials. A research assistant will help them use the system and offer counseling/explanations for the materials. The patient and caregiver will be given a week to learn these materials. Further counseling/explanations will be given, if necessary. After a week, the research assistant will ask the participants whether they have further questions on the educational materials. The research assistant will answer their remaining questions until the participants are satisfied with the explanations. Then the participants will be asked to take the computerized knowledge testing system again. Further educational materials will be offered, if necessary. The testing and educational procedures will continue until the participants' stroke and OT knowledge has reached a satisfactory level. The research assistant will make sure that the participants understand all the fundamental knowledge of stroke and OT, which will be pre-determined by our experts.

We expect that the whole procedure will take about 2 to 3 weeks (i.e., two to three times of education). The time that the patient/caregiver devotes to learning the related materials will be recorded. We will also document the difficulties/questions raised by the participants. Such information will be useful for further improving the efficiency the system.

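### The cost-per-QALY formula names no adjustment for baseline EQ-5D, and the only adjustment rule in Phase 6 is triggered by a significance test and not linked to the QALY difference

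*Protocol*

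**What the plan says.** The economic analysis is described in section (E), Phase 6.

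- **Effect measure (Procedure):** "The effects will be expressed as quality-adjusted life years (QALYs), which are measured by the EQ-5D".
- **Ratio (Procedure):** "The incremental cost-effectiveness ratio will be calculated by dividing the mean difference in costs by the mean difference in effect". The comparison is between the two groups, and no covariate is named.
- **Ratio (Data analysis):** "Incremental cost-effectiveness ratios will be calculated as cost per QALY to assess the cost-effectiveness of the different programs". Again no covariate is named.
- **Visits (Procedure):** "All participants will be assessed by trained raters at the beginning of the study, 4 weeks after inception of the study", then at 3 months and 1 year.
- **EQ-5D:** it is listed under Secondary outcome measures, with the remark that "The advantage of the EuroQol is that it can be transformed into a utility score, allowing cost-utility analysis".
- **Effectiveness analysis (Data analysis):** a "comparison of the change scores between time 2 to time 1 and time 3 to time 2 in primary and secondary outcome measures", by ANOVA, with ANCOVA added where a baseline difference is significant.

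Baseline EQ-5D is thus collected by implication: everyone is assessed at the start, the EQ-5D is a secondary outcome, and change from time 1 is analysed for secondary outcomes. Costs come from a diary covering 24 weeks. The horizon for the QALYs is not stated.

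**The concern.** A patient's utility at entry predicts that patient's later utilities, and hence the QALYs. When the arms differ by chance at baseline, part of that difference reappears in the QALY difference. Regression on baseline utility removes most of this. The formula as written does not call for it, and the rule that might supply it depends on a baseline test and is stated for the outcome comparisons, not for the ratio.

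Cost-effectiveness and cost-utility are a stated Phase 6 aim. The control arm also receives additional therapy, so a small QALY difference is plausible. With a small denominator, a shift of a few hundredths of a QALY can change the ratio a good deal. If adjustment is left unstated, it could also be chosen after the results are known.

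**Working it through.** **Inputs from the protocol.** 50 patients per arm, with about 70% expected to complete: 50 × 0.70 = 35. Visits at 0, 4 weeks, 3 months (taken as week 13) and 1 year (week 52). Alpha 0.05, taken as two-sided.

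**The plan's own figure.** The protocol gives no number for the QALY difference or its precision. Its only related figure is about 50 per arm for 2 Barthel points at 80% power. No SD is stated; 50 is reproduced if the SD is about 2.95 (35 per arm, and 35 / 0.70 = 50). Nothing below depends on this.

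**Assumptions not in the documents.** Utility SD 0.25 (range 0.20 to 0.30), the same at every visit; equal correlation ρ between visits of 0.3, 0.5 or 0.7; QALYs by the trapezoid rule over one year.

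**Step 1: weight of each visit.** Baseline (4/2)/52 = 0.038; week 4 (13/2)/52 = 0.125; week 13 (48/2)/52 = 0.462; week 52 (39/2)/52 = 0.375.

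**Step 2: size of a chance imbalance.** SE of the baseline difference = SD × √(2/n). For n = 50: 0.25 × √(2/50) = 0.050. For n = 35: 0.25 × √(2/35) = 0.060.

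**Step 3: carry-over.** Slope = 0.038 + ρ × 0.962, which is 0.33, 0.52 and 0.71. The direct part is only 0.038 × 0.05 = 0.002 QALY; the rest comes through correlation with later visits. Shift in the QALY difference for a one-SE imbalance:

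| | ρ = 0.3 | ρ = 0.5 | ρ = 0.7 |
|---|---|---|---|
| n = 50 | 0.016 | 0.026 | 0.036 |
| n = 35 | 0.020 | 0.031 | 0.043 |

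With SD from 0.20 to 0.30 the range is 0.013 to 0.043 for n = 50 and 0.016 to 0.051 for n = 35.

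**Step 4: a 24-week horizon.** The later weights then sum to 0.423, so the slope is 0.038 + ρ × 0.423 = 0.17, 0.25 and 0.33. Times 0.05 this gives 0.008, 0.013 and 0.017 QALY, roughly half the one-year figures.

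**Step 5: what the significance trigger would catch, if applied to EQ-5D.** Under randomisation a 0.05 test fires in about 5% of trials. Imbalances up to about 0.10 (n = 50) or 0.12 (n = 35) stay unadjusted and leave shifts of up to 0.03 to 0.07 or 0.04 to 0.08 QALY, depending on ρ.

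**Step 6: precision.** Standard error of the one-year QALY difference at SD 0.25, from 8,000 simulated trials per case:

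| n per arm | ρ | No adjustment | ANCOVA only if significant | Regression on baseline always |
|---|---|---|---|---|
| 50 | 0.3 | 0.038 | 0.037 | 0.034 |
| 50 | 0.5 | 0.042 | 0.040 | 0.033 |
| 50 | 0.7 | 0.045 | 0.041 | 0.028 |
| 35 | 0.3 | 0.044 | 0.043 | 0.040 |
| 35 | 0.5 | 0.049 | 0.046 | 0.039 |
| 35 | 0.7 | 0.054 | 0.049 | 0.033 |

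Regression in all cases cuts the standard error by about 9% (ρ = 0.3), 22% (ρ = 0.5) and 38% (ρ = 0.7). The unadjusted QALY difference correlates 0.42, 0.62 and 0.79 with the baseline difference.

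**The case against.** The strongest reply is that the protocol does not fix an unadjusted estimator. It gives the textbook definition of the ratio, and a regression-based arm difference is also a mean difference. Section (F), Anticipated challenges, says the team will seek advice on calculating QALYs, and covariates are often settled in an analysis plan, which is not available here. This stands: a reader might infer that adjustment has been ruled out, but the text only fails to mention it.

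Second, the ratio appears in the same Data analysis section as the ANCOVA rule, so the rule might be meant to cover it. The text does not say so, and Step 6 shows that the triggered rule recovers little.

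Third, the effect might be meant as change from baseline. The planned change scores stop at 3 months, however, and the second of them does not involve baseline. Subtracting baseline in full also over-corrects: on the same assumptions with n = 50, the QALY difference net of baseline has a standard error of 0.048, 0.040 and 0.031, worse than regression throughout and worse than no adjustment at ρ = 0.3.

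Fourth, the unadjusted difference in a randomised trial is unbiased over repeated randomisations, and its standard error already includes chance imbalance. That is right, and the point is limited accordingly. A reader might infer that baseline imbalance passes whole into the denominator. It does not: the direct weight is about 4% and the total carry-over about 0.3 to 0.7. Nor does the argument touch the cost difference. Instability and ambiguous sign belong to any such ratio, and baseline adjustment cures neither.

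**Conclusion.** The point holds as a matter of precision. Followed as written, the two economic passages give a QALY difference that makes no use of a baseline measurement the trial already has, and the only adjustment rule neither refers to that difference nor would often apply. A one-SE imbalance at 50 per arm shifts the denominator by about 0.016 to 0.036 QALY over one year, or roughly half that over 24 weeks, and the avoidable excess in the standard error is modest at low correlation and substantial at high correlation. These sizes rest on the assumed utility SD, the correlations and the trapezoid rule; the protocol supplies only the sample size, the completion rate and the visit times.

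The harm is extra variance and bias conditional on the imbalance that happens to occur. The documents do not support calling the planned ratio systematically biased, and the expected cost-effectiveness in Anticipated Results is a forecast with no decision rule attached. The change is worth making because it is simple and costs almost nothing.

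**What to change.** Add one sentence to the Phase 6 Data analysis section: the QALY difference used in the incremental cost-effectiveness ratio is estimated by linear regression of QALYs on arm with baseline EQ-5D utility as a covariate, whatever the baseline comparison shows. State in the same place the QALY horizon and how QALYs are built from the visits, since the size of the gain depends on both. Refer to this sentence where the ratio is defined under Procedure, so that the two passages agree.

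The cost is a change of wording and a little programming; no new data or visits are required. A joint bootstrap of the cost and QALY differences, or incremental net benefit alongside the ratio, would be an optional reporting addition.

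### The Phase 6 costing has no cost line or unit cost for the research-assistant time that delivers the education component, so the plan as written would understate the programme's delivery cost

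*Protocol*

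**What the plan says.** All references are to section (E) of the protocol unless noted.

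- **Cost categories** (Phase 6, Procedure): "The costs include the costs related to resource use of primary care clinicians, secondary care appointments, admissions to health care facilities, community-based support" and out-of-pocket spending. Medication, assistive devices and home adaptations are added. On the basis of the estimates: "The direct cost estimates will be based on the costs of hospital stay and follow-up rehabilitation care".
- **Staff time** (same place): "The hourly costs of specialists (including physicians, physical therapists, occupational therapists, and speech and language therapists) will be calculated" from the hospital's salary schedules. Recording rests on "having each patient keep a cost diary for the first 24 weeks after randomization", which a research assistant checks and which covers items "including the time spent on each kind of professional care".
- **General statement** (same place): "The cost of each group will be recorded".
- **Therapist input, experimental arm** (same place): a six-week programme with an expected 2 to 4 therapist hours per patient per week.
- **Control arm** (same place): "For the control group, we will provide 2-hour OT per week in addition to the original OT", with no number of weeks. The later treatment-protocols text puts the added rehabilitation at about 2 hours a week for 3 weeks, matched to participation time in the experimental arm.
- **Education component** (Phase 6, treatment protocols): "A research assistant will help them use the system and offer counseling/explanations for the materials". The assistant also answers questions, repeats the cycle and confirms that the fundamentals are understood, over about two to three weeks. The learning time of the patient or caregiver is recorded; assistant time is not mentioned.

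**The concern.** Cost-effectiveness is a stated Phase 6 aim, and section (F) anticipates that the programme will prove cost-effective. The background section names limited staff and time as an obstacle to patient-centred care, so the staff time needed to deliver the education is central to the economic question. Yet the person who delivers it belongs to no category in the cost list and to none of the professions given an hourly rate. Outside the trial, someone would have to be paid for that work. If it is left out, the programme's incremental cost comes out too low. Hours not logged while the trial runs cannot be recovered reliably afterwards, so this is a data-collection question as well as an analysis detail.

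**Working it through.** The protocol states no cost, salary, quality-adjusted life-year value or cost-effectiveness ratio, so there is no figure to reproduce. The check is arithmetic on hours.

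**Inputs from the protocol**
- Experimental therapist time: 6 weeks × 2 to 4 h = 12 to 24 h per patient.
- Control extra occupational therapy: 3 weeks × 2 h = 6 h under the treatment-protocols text, or 6 weeks × 2 h = 12 h if the weekly figure under Procedure runs for the programme's six weeks.

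**Inputs assumed, because the protocol gives none**
- Assistant delivery time: 2 to 6 h per experimental patient, additional to the therapist hours. The upper value is the protocol's matched participation time (2 h × 3 weeks = 6 h). That time includes self-study, so the true figure is probably lower.
- Assistant hourly rate: 0.5 to 1.0 of the occupational therapist rate.
- Assistant time in the control arm is set to zero here. The protocol allows some, so the between-arm increments below are slightly too high.

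**Step 1: therapist hours only.** Increment = experimental − control.
- Lowest: 12 − 12 = 0 h.
- Highest: 24 − 6 = 18 h.

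**Step 2: value of assistant time.** Added time = hours × rate ratio.
- Lowest: 2 × 0.5 = 1 therapist-hour equivalent.
- Highest: 6 × 1.0 = 6 therapist-hour equivalents.

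**Step 3: increment with assistant time included.**
- Lowest: 0 + 1 = 1 h.
- Highest: 18 + 6 = 24 h.

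**Step 4: share of experimental delivery time left out.** Share = added ÷ (therapist hours + added).

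| Therapist hours | Added | Share omitted |
|---|---|---|
| 24 | 1 | 1/25 = 4.0% |
| 12 | 1 | 1/13 = 7.7% |
| 24 | 6 | 6/30 = 20.0% |
| 12 | 6 | 6/18 = 33.3% |

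**Step 5: effect on the difference between arms.** With 12 h against 6 h, the 6 h increment grows by 1/6 = 17% to 6/6 = 100%. With 12 h against 12 h, a difference of 0 h becomes 1 to 6 h. The unresolved duration of the control arm's extra therapy moves the increment by 12 − 6 = 6 h, as much as the largest assumed assistant time.

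**The case against.** The protocol never says that assistant time is excluded. The list of costed specialists opens with a word that makes it non-exhaustive, the diary covers every kind of professional care, and the costs of both groups are to be recorded. The only description of the assistants' profession, in Phase 2, is occupational therapist or research nurse; if Phase 6 assistants were occupational therapists, a listed rate would apply. Phase 5 places the education system inside the patient-centred programme, so some assistant contact might overlap with the 2 to 4 weekly therapist hours. Section (F) promises advice from a health-economics expert, and detailed costing schedules often sit in a separate plan.

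Part of this stands. Exclusion is an inference, and the size depends on the time being additional. But every named example is a clinician, the Phase 2 description is not carried into Phase 6, and research nurses have no listed rate, so the same task could be costed or free depending on who performs it. The general statement on costs is itemised in the paragraph that follows it, and no item there covers the assistant. A later analysis plan cannot supply hours that nobody logged.

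A reader might infer that contact time is charged to the control arm while the matched time is free in the experimental arm. The protocol does not support that. The experimental arm's 12 to 24 therapist hours can be costed by the same rule as the control arm's 6 to 12 extra hours and are at least as many. Control participants also receive some explanations from the assistant.

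**Conclusion.** The point holds as a gap in the costing of the education component. As written, the plan has no cost line, no unit cost and no stated record for the assistant time that delivers it, and following it would understate the programme's delivery cost and so the incremental cost. Under the stated assumptions (2 to 6 additional hours at 0.5 to 1.0 of the occupational therapist rate), the omitted part is about 4% to 33% of experimental delivery time in therapist-hour equivalents. The share of total cost would be smaller, because hospital stay, admissions, medication and devices also count.

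A reader might go further and conclude that the cost-effectiveness ratio is biased by a known amount. The documents do not allow that. Without salaries, total costs or utility differences, no effect on the ratio can be computed. Omitting a programme cost raises apparent net benefit whatever the sign of the effect, but it lowers the ratio itself only if the quality-adjusted life-year difference is positive.

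**What to change.** 1. Log research-assistant delivery time per patient in both arms: help with the system, counselling, explanations and repeat rounds. Exclude research-only tasks such as diary checks and outcome testing.
2. Add this time to the Phase 6 cost list, valued at the hospital salary rate of the staff who would deliver it in routine care, and use it in the base-case ratio. State whether it is additional to the 2 to 4 weekly therapist hours.
3. Reconcile the two Phase 6 statements on the duration of the control arm's extra therapy, because the cost increment depends on it.

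The cost is one more field in the time log and one line in the cost list. The resulting ratio may be slightly less favourable to the programme.
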